#### 7.1.6 Conventions for Missing Concomitant Medication / Medical History Dates

Missing or partial start dates for concomitant medications (CM) / medial history (MH) will be imputed similarly to the strategy given in section 7.1.5.

For end dates for concomitant medications, the following methods will be used to impute missing or partial dates:

- CM/MH end date month/year available and day missing:
  - The last day of month is to be used to impute the end date.
- CM/MH end date year available and month/day missing:
  - The December 31 is to be used to impute the end date.
- CM/MH end date completely missing:
  - The last visit date is to be used to impute the end date.

Note: The imputed date will not be beyond the patient's last visit date.

### **7.1.7 Conventions for Missing Other Analysis Dates**

In order to derive 3-month intervals for efficacy or safety analysis, the following methods can be used to impute missing or partial start dates:

- Start date month/year available and day missing:
  - If the month and year are the same as those in the first dose date of ENANTONE treatment or study day -93, then the first dose date or study day -93 is to be used to impute the start date.
  - If the month and/or year are different from those in the first dose date of ENANTONE treatment or study day -93, then first day of the month will be used for the start date.
- Start date year available and month/day missing:
  - If the year is the same as those in the first dose date of ENANTONE treatment or study day -93, then the first dose date or study day -93 is to be used to impute the start date.
  - If the year is not the same as the year of the first dose date of ENANTONE treatment or study day -93, set the start date as January 1.

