#### 7.1.1 Study Definitions of Baseline and Change from Baseline

Baseline, for the ENANTONE period, is defined as the last non-missing measurement prior to the first dose of ENANTONE treatment. Unless specified otherwise, baseline values for variables related to CPP will be limited to values collected no more than 3 months (93 days), inclusive, prior to the first dose of ENANTONE.

The change from baseline will be calculated for the treatment period by subtracting the baseline values from the individual post-baseline values. If either the baseline or post-baseline value is missing, the change from baseline is set to be missing as well.

Data from the follow-up period after completion of treatment period, will be analyzed separately and the baseline for the follow-up period will be defined as the first non-missing measurement after the last dose of GnRHa treatment (with either ENANTONE or another GnRHa).

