#### 7.1.4 Conventions for Incomplete or Missing date of ENANTONE Therapy

The date of the first ENANTONE administration is necessary for establishing the chronology of all subject data. Likewise, the date for the last administration of ENANTONE has similar importance for indexing subject data. If the month and year are available but the day of administration is missing, an imputed date will be used in the derived data. The imputed day will be in the middle of the month with a date of the 15th of that month chosen as the imputed date. The imputed values will be documented in the data listings alongside the actual recorded date. Because dose scheme may be complicated, based on clinical judgement, other unpredicted special cases will be handled in program with notes documented in the original SAS programs.

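### SAP 7.1.7 places partly dated assessments with an earliest-date rule; year-only values can lose their baseline or window place, become baseline-eligible, or shift by up to four (at most five) windows

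*SAP*

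**What the plan says.** SAP 7.1.7 covers dates needed to form the 3-month intervals for efficacy or safety, and says that "the following methods can be used to impute missing or partial start dates". It has two branches.

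- **Day missing.** If the month and year match those of the first dose or of Day -93, "then the first dose date or study day -93 is to be used to impute the start date". Otherwise, "then first day of the month will be used for the start date".
- **Month and day missing.** The condition is "If the year is the same as those in the first dose date of ENANTONE treatment or study day -93", with the same two anchors. For any other year, "set the start date as January 1".

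These dates feed other definitions:

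- SAP 7.1.1 defines baseline as "the last non-missing measurement prior to the first dose of ENANTONE treatment", and for CPP variables limits it to the 93 days before that dose, inclusive.
- SAP 7.1.2 makes the first dose Day 1.
- SAP Table 1 opens the first window (Month 3) at Day 46.
- SAP 7.1 starts the treatment phase at the first dose. SAP 7.8.1 takes the end-of-treatment Tanner result from the last observation in that phase.

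For missing days of ENANTONE administration, SAP 7.1.4 uses a different convention: "The imputed day will be in the middle of the month".

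**The concern.** The rule has the same structure as the adverse-event rule in SAP 7.1.5, with Day -93 added. Section 7.1.5 limits its rule to deciding whether an event began before or after the first dose. An early anchor is a usual choice for that question. Section 7.1.7 asks something else: which 90-day window a measurement belongs to, and whether it is baseline. An anchor at the start of the possible range answers that badly.

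Every change from baseline depends on the baseline chosen, and every 3-month summary of Tanner stage, hormones, bone age ratio and growth depends on the window. The study has about 100 subjects summarised by sex, so some cells will be small and a few misplaced records could show. The index period goes back to 1998, and the SAP writes four separate conventions for incomplete dates, so it expects some.

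**Working it through.** **Check of the window grid.** For window k = 1 to 20, target = floor(91.25k), lower = 90k - 44, upper = 90k + 45. This reproduces all 20 rows of SAP Table 1. For k = 1 it gives 91, 46 and 135. Each window is 90 days wide, and Days 1 to 45 belong to none.

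The 7.1.7 rule was then applied to every first-dose date in 2010 (and in 2012 as a leap year), with true assessment dates from 400 days before to 1,099 days after the first dose. Percentages below use 2010 and assume that assessment dates are spread evenly over that range. They are shares of possible dates, not of study data.

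**1. Values moved to the first dose date.** Day 1 is not before the first dose, so it is not baseline, and it is below Day 46, so it is in no window.
- Day missing, first-dose month: all values go to Day 1. Of 11,111 date pairs, 5,373 (48%) are true pre-dose dates that lose baseline eligibility.
- Year only, first-dose year, first-dose anchor: of 365 × 365 = 133,225 pairs, 51,360 (38.6%) are true Month 3 to Month 12 values that leave every window, and 29,574 (22%) are eligible baseline values that are lost.

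**2. The unresolved choice of anchor.** The first dose and Day -93 never share a calendar month, so the day-missing branch is unambiguous. They share a calendar year when the first dose falls on day-of-year 94 or later (4 April to 31 December): 365 - 93 = 272 dates, and 272/365 = 74.5%.
- If Day -93 is chosen, values up to Day 272 (273 in a leap year) become baseline-eligible. On-treatment values are 37,128 of 272 × 365 = 99,280 ambiguous pairs (37%).
- Example: first dose 15 September 2010, so Day -93 is 14 June 2010. A result of 20 December 2010 (Day 97, Month 3) recorded only as 2010 may be placed on Day -93.
- The Day -93 anchor also makes values eligible that are too old for baseline: by up to 30 days when the day is missing (Day -123 becomes Day -93), and by months when only the year is known.

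**3. January 1.** The shift is 0 to 364 days (365 in a leap year), with a mean of 364/2 = 182 days for an evenly spread true date. Among 333,715 pairs whose true date lies in a window:

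| Result | Pairs | Share |
|---|---|---|
| Correct window | 47,156 | 14.1% |
| One window early | 86,760 | 26.0% |
| Two | 78,660 | 23.6% |
| Three | 70,560 | 21.1% |
| Four | 35,419 | 10.6% |
| Five | 90 | 0.03% |
| No window (before Day 46) | 15,070 | 4.5% |

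- Four windows: first dose 15 September 2010, true date 20 December 2011 (Day 462, Month 15), recorded as 2011, becomes Day 109 (Month 3).
- Five windows: first dose 21 February 2010, true date 28 December 2011 (Day 676, Month 24), becomes Day 315 (Month 9).
- Phase change: in the first of these examples, assume that the last dose was on 15 June 2011 (Day 274). The treatment phase then ends at about Day 274 + 45 = 319. The true Day 462 value is follow-up, and its imputed Day 109 is on treatment.

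**4. Day missing, other months.** Moving to the first of the month shifts a value by at most one window, or out of Month 3 into no window. From 60 days after the first dose onward, the first of the month gives the wrong window in 15.9% of cases, and the 15th in 8.1%.

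**The case against.** Much of the opposing case stands.

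- **The large effects need a year-only date.** With only the day missing, the shift is small and no on-treatment value can become baseline.
- **On-treatment to baseline is a narrow path.** It also needs the Day -93 reading and no later eligible value, because baseline is the last non-missing one and Day -93 is the earliest eligible day. Protocol 10.4.1 requires pre-treatment records of Tanner stage, hormones and bone age, so a competing value will often exist, although that criterion does not require it within 93 days.
- **A reader might infer that values moved to Day 1 are discarded.** The documents do not support that. SAP 7.1 keeps them in the treatment phase, they are listed, and they could still be the last observation. They are lost only to baseline and the windows. The note to SAP Figure 4.a even labels the first day of administration as baseline.
- **A reader might take 74.5% as the share of data affected.** It is a share of calendar dates. The protocol points to dated sources: X-ray dates (10.2.2.5), visit dates (10.2.2.18), and checks and queries for missing or unclear data (10.6.1).
- **The end-of-treatment Tanner analysis does not use windows.** The inclusion criteria also call for an end-of-treatment record, which would usually displace a value pulled forward from follow-up.
- **The study is descriptive and not powered for testing** (Protocol 10.9).

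The permissive wording of 7.1.7 is a weaker defence. It leaves the choice of anchor to whoever programs the tables and gives no criterion.

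**Conclusion.** The rule as written misplaces assessments, and this follows from SAP 7.1.1, 7.1.2, 7.1.7 and Table 1 alone. For year-only dates it can remove a value from baseline and all windows, make it baseline-eligible through an unresolved choice open for 272 of 365 first-dose dates, or move it by up to four windows (five at the extreme), sometimes across the phase boundary. For day-missing dates the fault is milder: at most one window, plus loss of baseline eligibility for true pre-dose values in the first-dose month.

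The documents do not support saying that results are biased by a given amount, or that on-treatment values will routinely serve as baseline. The number of partial dates, and how many are year-only, is not given. The 3-month summaries are exposed directly, and the end-of-treatment result mainly through baseline. The point merits a change because the misplacement is demonstrable and the correction is cheap.

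**What to change.** For assessments, delete the two-anchor rule and the January 1 rule in SAP 7.1.7, and replace them with:

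1. **Year only.** List the value. Do not use it for baseline or windowed summaries. Use it for end of treatment only if the whole calendar year lies inside the treatment phase and no later on-treatment record exists.
2. **Day missing, month other than the first-dose month.** Impute the 15th, as SAP 7.1.4 does for dose dates, bounded by known phase dates.
3. **Day missing, first-dose month.** Classify the value as pre- or post-dose only where the chart shows the order, and impute on that side of the first dose. Otherwise list it only.

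Item 3 is needed because the 15th alone would create a new error. In a 30-day month, a first dose on day 16 to 30 with a value on or after it gives 15 + 14 + ... + 1 = 120 of 900 date pairs (13%) in which a value from the dosing day or later would be moved before dosing. The present rule produces none of these.

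The cost is SAP wording and minor programming. A few records leave the baseline or windowed tables, and the 15th still misplaces some values (8.1% against 15.9%, for evenly spread dates). A count of day-missing and year-only assessment dates would show how much the change matters.

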## **7.2 Analysis Sets**

- Safety Analysis Set (SS): The SS consists of all enrolled subjects.
- Full Analysis Set (FAS): The FAS consists of all enrolled subjects.
- Per Protocol Analysis Set (PPS): The PPS consists of all subjects who are in the FAS and have no major protocol deviations. If 5% or more of the FAS set are found to have violated some of the study criteria then repeat analysis will be performed on the Per Protocol Set.

## **7.3 Disposition of Subjects**

The number and percentage of subjects, that complete ENANTONE therapy will be tabulated. Otherwise the reasons for not completing ENANTONE therapy will be tabulated. Subjects receiving other GnRHa therapies will be tabulated, and these other therapies will be tabulated, if possible.

The number and percentage of subjects as shown below will also be tabulated.

- Number of subjects
  - Total number of subjects in the ENANTONE treatment period
- Number and percentage of subjects in the follow-up phase after completing treatment with ENANTONE
  - Percentage who had been treated with only ENANTONE
  - Percentage who had been treated with ENANTONE in the treatment phase and then another GnRHa in the follow-up period
- Number and percentage of subjects who completed puberty in the follow-up phase

Puberty is defined as having a Tanner Stage = V after completion of GnRHa therapy with either ENANTONE only or ENANTONE followed by another GnRHa after ENANTONE

The following categories for the reason of primary discontinuation of ENANTONE therapy will be presented for this study.

- Lack of efficacy
- Adverse Event
- Change CPP therapy to another GnRH agonist
- Investigator Judgment
- Other

When the subject meets the protocol's eligibility criteria (inclusion criteria) and is henceforth enrolled into the study, the subject's missing data –if not satisfactory to fulfil a complete analysis for primary and secondary endpoints– will not be regarded as protocol deviation.

#### **7.4 Demographic and Other Baseline Characteristics**

Patient demographics will be summarized using descriptive statistics on the safety analysis set. Individual subject demographics will be listed.

- Age at Date of Diagnosis of CPP (derived determining number of days between date of birth and date of diagnosis divided by 365.25 to obtain age in years).
- Age of appearance of secondary sexual characteristics
- Age at start of ENANTONE therapy
- Gender
- Family Origin from Northern or Southern China
- Height
- Weight
- BMI

The following baseline information prior to the initiation of ENANTONE therapy will be presented for this study as included in the analysis of the Change from Baseline in these parameters during the ENANTONE treatment period.

- Tanner Stage
- Random LH
- Random FSH
- LH and FSH for each time point during a GnRH stimulation test
- Peak LH during a GnRH stimulation test
- Peak FSH during a GnRH stimulation test

- Estradiol
- Testosterone
- Bone age
- Bone age/chronological age

The Bone age to Chronological age ratio is determined using birthdate and date of the bone age assessment to obtain age in days and then divided by 365.25 to obtain age in years, not truncated to an integer. Individual chronological age values will be reported to 1 decimal and mean values to 2 decimal places.

- Predicted Adult Height
- Bone Mineral Density (BMD)
- Linear growth rate
- Cranial CT or MRI

## 7.5 Medical History and Concurrent Medical Conditions

Medical history includes clinically significant diseases and surgeries. Conditions ongoing at the time of ENANTONE treatment are considered concurrent medical conditions.

Medical history and concurrent medical conditions will be coded using the Medical Dictionary for Regulatory Activities (MedDRA version 21.0), and will be tabulated based on safety analysis set. And system organ class (SOC) terms will be sorted by alphabetical order and preferred terms will be sorted in decreasing frequency based on the total number of all subjects.

Individual medical history and concurrent medical conditions data will be listed.

## 7.6 Medication History and Concomitant Medications

Medication start and stop dates will be compared to the date of first dose of ENANTONE and will be classified as medications taken prior to, concomitant with and concomitant after ENANTONE.

Prior medications are those medications that start and stop prior to the date of first dose of study treatment. Concomitant medication with ENANTONE is any drug given in addition to the study medication, ENANTONE, and defined as those medications that are given on or after the first day of study treatment during the ENANTONE treatment phase. Medication given after ENANTONE is defined as those medications that are given on or after the last dose of ENANTONE and during the follow-up phase. Medications will be classified according to the World Health Organization Drug Dictionary (WHODRUG) and tabulated by WHO drug Anatomical Therapeutic Chemical (ATC) classification based on the safety analysis set. ATC will be sorted using alphabetical order and preferred medication names will be sorted by decreasing frequency based on the total number of all subjects.

Individual subject medication history and medication data will be listed.

## 7.7 Study Drug Exposure

The following duration of study observations will be summarized (definitions for each are provided later).

- Duration of study observations
  - Duration of observations of CPP diagnosis to end of follow-up period
  - Duration of from 1st dose of ENANTONE to end of treatment period

Similarly, the following duration of the follow-up period will be summarized.

- Duration of the follow-up period for all subjects
- Duration of the follow-up period from last dose of ENANTONE to end of follow-up period for patients who received ENANTONE treatment only
- Duration from start of other GnRHa therapy from 1st dose of GnRHa to the end of the GnRHa treatment
- Duration of the follow-up period for those who were treated with another GnRH agonist during this period, from the last dose of GnRHa to the end of follow-up period, if patient receive another GnRHa

Duration of ENANTONE treatment (defined as time since first administration of ENANTONE treatment in months) will be summarized for the ENANTONE treatment phase. The duration of ENANTONE treatment will be calculated as:

*(Date of 45 days, inclusive, after the last administration of ENANTONE or date of first dose of a non-ENTANTONE GnRHa therapy – Date of first administration of ENANTONE. + 1)/30.44*

Duration of Non-ENANTONE GnRHa treatment (defined from the first dose of a non-ENTANTONE GnRHa therapy to the last dose of any GnRHa other than ENANTONE, even if the treatment changes.) will be summarized, if possible, in Non-ENANTONE follow-up phase:

*(Date of last administration of any GnRHa other than ENANTONE – Date of the first administration of a non-ENTANTONE GnRHa therapy + 1)/30.44*

Descriptive statistics will be determined for duration of time during the ENANTONE Treatment phase while on ENANTONE treatment, and the duration of time during the follow-up Phase while on other CPP treatment (if applicable) and the duration of follow-up interval after completion of GnRHa therapy for CPP by sex group.

Time Interval of duration of ENANTONE treatment will be tabulated by sex group during the ENANTONE treatment phase for the following time intervals:

- ≥9 months, ≥12 months, ≥18 months, ≥24 months, ≥30 months, ≥36 months, ≥42 months, ≥48 months, ≥54 months, ≥60 months, etc.

The days on ENANTONE treatment is the number of days between first and last ENANTONE injection plus 45 days unless the subject had been on GnRHa in which case this is not 45 days but is the date when they received the 1st dose of the GnRHa. Descriptive statistics of days will be displayed by sex group during the ENANTONE treatment phase.

A by-subject listing of duration of ENANTONE treatment, other CPP treatment during the follow-up interval, duration of follow-up interval after completion of GnRHa therapy for CPP will be provided.

No inferential analysis for comparison duration between sex group will be performed.

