10.7 Data Analysis

The clinical effective therapeutic dose as well as safety and effectiveness data of leuprorelin acetate used for the treatment of CPP will be summarized primarily using descriptive statistics; however inferential methods may be used to provide covariate adjustment as well as an indicator of data strength. To support the study objectives the primary data summaries will be focused on the ENANTONE treatment phase and the follow-up phase. The definition of each of these phases will be developed in the SAP. If more than 5% of subjects have CPP treatment with a generic GnRHa after ENANTONE then complimentary safety summary tables will be presented on those data from that therapy.

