## 7.0 METHODS OF ANALYSIS AND PRESENTATION

### 7.1 General Principles

Statistical analysis will be performed using SAS® software (SAS Institute, Inc., Cary, North Carolina) Version 9.2, or later.

Data will be associated and summarized by the following:

- ENANTONE treatment phase includes all data from the first dose of ENANTONE up to and including either 45 days, inclusive, after the last dose or date of first dose of a non-ENTANTONE GnRH agonist therapy (earliest case scenario)
- Follow-up phase includes all data after the above defined ENANTONE treatment phase. If the subject continued treatment for CPP with another GnRH agonist after ENANTONE, their data from the follow-up period will be reported separately from those who only received ENANTONE for the treatment of CPP.

Unless specified otherwise, all data summaries will be performed for the following groups: Male, Female and Total, and will be presented during the ENANTONE treatment phase and results during the follow-up phase. Continuous variables will be summarized including the number, the mean, the standard deviation, median, minimum and maximum. Categorical variables will be summarized including the number and percentage of subjects.

Confidence intervals will be reported as 2-sided 95%, unless otherwise stated.

Means and medians will be presented to 1 more decimal place than the recorded data and standard deviations (SDs) will be presented to 2 more decimal places than the recorded data. Confidence intervals about a parameter estimate will be presented using the same number of decimal places as the parameter estimate. Derived variables may exhibit excessive decimal precision therefore, derived variables may be rounded to a precision representative of the expected data and means, SD and individual values will be formatted in a similar manner as described above.

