## **7.11 Safety Analysis**

Safety data will be summarized using the safety analysis set, and individual data will be presented in data listings. Safety outcomes will be analyzed by ENANTONE treatment (high, low dose and overall), and unless specified otherwise will not be stratified by sex. Separate summaries will be performed for the ENANTONE treatment phase and the different segments of the follow-up phase described in section 7.8.

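### Switch-day adverse events fall in the ENANTONE phase, and the boundaries for the end of other-GnRHa treatment and the start of follow-up are missing or conflict

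*SAP*

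**What the plan says.** - **Phase assignment (SAP 7.1).** "ENANTONE treatment phase includes all data from the first dose of ENANTONE up to and including either 45 days, inclusive, after the last dose". The alternative end point is the day on which another GnRHa was first given. The earlier date applies, and that end day belongs to the phase. Then: "Follow-up phase includes all data after the above defined ENANTONE treatment phase".
- **Durations (SAP 7.7).** ENANTONE duration ends at "Date of 45 days, inclusive, after the last administration of ENANTONE or date of first dose of a non-ENTANTONE GnRHa therapy", less the first-dose date, plus one day. Other-GnRHa treatment is "defined from the first dose of a non-ENTANTONE GnRHa therapy to the last dose of any GnRHa other than ENANTONE", also plus one day. Follow-up duration starts at the last ENANTONE dose for ENANTONE-only children and at the last GnRHa dose for switchers.
- **Follow-up baseline (SAP 7.1.1).** The first available value after the last dose of whichever GnRHa came last.
- **Follow-up segments (SAP 7.8).** If data permit, results during other-GnRHa treatment and after its completion are shown separately. No day rule divides the two.
- **Safety (SAP 7.11).** "Separate summaries will be performed for the ENANTONE treatment phase and the different segments of the follow-up phase described in section 7.8". SAP 7.11.1 makes adverse events per 100 person-years the primary safety outcome.
- **Protocol 10.7.** The phase definitions are left to the SAP. If more than 5% of subjects had a generic GnRHa after ENANTONE, "complimentary safety summary tables will be presented on those data from that therapy".

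**The concern.** A rate per person-year needs its events and its time cut at the same points. Here the day of the switch injection gives its events to ENANTONE but its time to both products. Injection site reaction is the adverse event that both documents name as an example in the primary safety outcome, and it is the type of event most likely to fall on that day. A reaction to another manufacturer's product would then enter the ENANTONE-phase rate.

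At the other end, ENANTONE keeps up to 45 days after its last injection as treatment, while the other product has no written carry-over. If the 7.7 duration is used as the boundary, events, hormone values and Tanner stages from the weeks just after a GnRHa injection would be reported as after completion of therapy. For ENANTONE-only children, the same weeks are treatment under 7.1 but follow-up under 7.7 and 7.1.1. Admitting children who later used another GnRHa was a main purpose of the protocol amendment, so these boundaries will be used.

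**Working it through.** The plan states no figure to reproduce. The check applies its day-count rules to worked timelines. The 28-day injection interval is in the protocol for leuprorelin; for another GnRHa it is an assumption.

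**1. How long is the ENANTONE tail?** Take 10 ENANTONE injections, on day 1 to day 1 + 9 × 28 = 253. The text of 7.7 gives days on treatment as last minus first plus 45: 252 + 45 = 297. The 7.7 formula gives:
- end day read as last dose + 44: 297 − 1 + 1 = 297, which agrees;
- end day read as last dose + 45: 298 − 1 + 1 = 298.

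So the inclusive 45 days can mean 44 or 45 days after the last dose.

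**2. Where does the switch day fall?**

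| First other-GnRHa dose after last ENANTONE dose | Day | ENANTONE phase ends | Switch day in ENANTONE phase? |
|---|---|---|---|
| 28 days | 281 | 281 | Yes |
| 45 days | 298 | 297 or 298 | Depends on the reading in step 1 |
| 60 days | 313 | 297 or 298 | No |

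A switch without a gap in 4-weekly treatment is the 28-day row.

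**3. Double counting.** In the 28-day row with 6 other-GnRHa injections, ENANTONE duration is 281 − 1 + 1 = 281 days. Other-GnRHa duration is 28 × 5 + 1 = 141 days. The sum is 422. The calendar span from day 1 to the last injection (day 281 + 140 = 421) is 421 days. The extra day is the switch day. Its events go only to ENANTONE, so k − 1 of the k other-GnRHa injection days remain in follow-up, and none if k = 1.

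**4. The missing tail.** With k injections, 7.7 gives 28(k − 1) + 1 days. The ENANTONE rule would add 44 (or 45).

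| k | 7.7 as written | With 44-day tail | Share left out |
|---|---|---|---|
| 1 | 1 | 45 | 98% |
| 3 | 57 | 101 | 44% |
| 6 | 141 | 185 | 24% |
| 12 | 309 | 353 | 12% |
| 24 | 645 | 689 | 6% |

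These are shares of treatment time, not changes in an event rate.

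**5. Net effect on a rate of injection-day events.** Assume a within-window switch, equal risk per injection, and 7.7 durations used as person-time. As written, the rate is proportional to (k − 1)/[28(k − 1) + 1]. Under matching rules with a 45-day tail it is k/[28(k − 1) + 46].
- k = 3: (2/57)/(3/102) = 1.19
- k = 6: (5/141)/(6/186) = 1.10
- k = 12: (11/309)/(12/354) = 1.05
- k = 1: no injection-day events remain, so the rate is 0

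The direction depends on k. Events spread evenly over time would not bias the rate.

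**6. ENANTONE-only children.** A value taken 28 days after the last dose is in the treatment phase (7.1), can be the follow-up baseline (7.1.1), and lies in time that 7.7 counts as follow-up. The 44 to 45 days are therefore counted in both durations.

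**7. Scale.** With about 100 subjects (SAP 6.0), the 5% trigger in Protocol 10.7 needs 6 children. If each had one other-GnRHa course and records running that long, the unassigned tail would be 6 × 44 / 365.25 = 0.72 to 6 × 45 / 365.25 = 0.74 person-years. The actual number of switchers is not given.

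**The case against.** The best defence is that little depends on this. The objectives concern ENANTONE, no comparison with another GnRHa is planned, and other-GnRHa results are conditional on the data. Misattribution is one day per within-window switcher and errs against the study drug. SAP 7.11.1 also tabulates ENANTONE-related events separately and lists every event. All of this stands and limits the size of the point. It does not repair the all-event rate, which is the primary safety outcome and follows a written rule that places another product's first-injection reactions in the ENANTONE phase.

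Three stronger readings are tempting, and the documents do not support them:

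- A reader might infer that ENANTONE gets 45 days and the switch day on top, and the other product neither. The 7.1 rule takes the earlier date: a child switching at 28 days has carry-over only to the switch, and a switch after the window leaves that day outside the phase. The 7.7 formula also counts the switch day as other-GnRHa time. The other product loses only that day's events.
- A reader might take it as SAP text that everything after the last other-GnRHa dose is off-treatment. SAP 7.7 defines a duration, and 7.11 refers to the segments of 7.8, which have no day rule. Off-treatment is the natural reading, supported by 7.7 and 7.1.1, but it is an inference.
- A reader might treat the shortened time in step 4 as the inflation of the adverse event rate. For within-window switchers this ignores the first-injection events already moved to ENANTONE. For any child it presumes that the 7.7 duration is the person-time, which 7.11.1 does not say.

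It is also fair that 7.1.1 treats both products alike. The fault there is conflict with 7.1, not asymmetry.

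**Conclusion.** The point holds in three parts. First, for within-window switchers, 7.1 puts switch-day adverse events in the ENANTONE phase while 7.7 counts the day for both products; later switchers are not affected. Second, other-GnRHa treatment has no carry-over in 7.7, and 7.8 and 7.11 state no boundary with the period after completion. Third, 7.1 conflicts with 7.7 and 7.1.1 on when follow-up begins for ENANTONE-only children.

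The first and third parts rest on the text. The off-treatment consequence of the second rests on the natural reading. The effect is small: at most one misattributed day per within-window switcher, and 44 to 45 days per switcher treated differently between products. Its effect on reported rates cannot be computed without the number of switchers and the other products' injection intervals. It is still worth correcting before analysis, because it is a stated rule in the primary safety rate and the correction is cheap.

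**What to change.** 1. For adverse events and person-time, end the ENANTONE phase on the day before the first other-GnRHa dose. Assign events with onset on the switch day, and that day, to the other-GnRHa segment, except events recorded as starting before the injection. Switch-day Tanner and hormone assessments may stay in the ENANTONE phase. In step 3 the durations then become 280 + 141 = 421 days, with no overlap.
2. State one end-of-treatment boundary for the other-GnRHa segment. By default use the same 45-day rule as for ENANTONE, or the last record if earlier, and start the after-completion segment the next day. Say whether the 45 days end at last dose + 44 or + 45.
3. Use these boundaries for events, person-years, the 7.7 durations and the 7.1.1 follow-up baseline, for ENANTONE-only children as well.

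The cost is SAP wording and a few derivation rules; Protocol 10.2.2.19 already collects the first and last dates of both treatments. The downsides are slightly less off-treatment follow-up and a 45-day window that may not suit products with other injection intervals. If the sponsor knows those intervals, it can justify a different analysis window, provided that it is written down and applied to events and time alike.
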